Cover Page

Title: Adhesive Tape Placement on Patients' Masks in the ED Increases Compliance of Proper Face Mask Use

[name]

11/9/2021

NCT04812184

Protocol ID IUMASKstudy

Study Design and Setting:

This study was an open-label randomized control trial at Eskenazi Hospital ED from April 2020 to October 2020. Eskenazi Hospital is a busy, urban, academic, level 1 trauma center in downtown Indianapolis serving a racially diverse, underserved population with over 100,000 annual ED visits. This study was approved by the Indiana University Institutional Review Board (protocol #2004425945) and registered on ClinicalTrials.gov (NCT04812184).

Selection of Participants:

Patients presenting to the ED were screened for enrollment by trained research personnel when one of the study authors was working. All patients in the ED were required to wear facial coverings by institutional policy, and patient-provided personal masks were acceptable. Patients were excluded if they were: (1) pregnant; (2) prisoners; (3) not English- or Spanish-speaking; (4) intoxicated or with decompensated psychiatric illness; (5) presenting to the ED with a life-threatening condition; (6) allergic to standard tape and/or tegaderm. Patients were approached and verbal consent was obtained in their private ED room, then participants were randomized to either the control or intervention arms by simple randomization.

Randomization:

The randomization sequence was generated by a computerized random number generator (simple randomization). The randomization assignment was concealed from the study team and was provided within our REDCap database only after participants had been enrolled and provided informed consent.

Interventions:

Participants in the intervention arm had standard surgical tape placed over the bridge of the nose to adhere to the top of the mask (Supplemental Figure 1). Control participants had no intervention. Participants were told the study was about PPE use, but no additional instruction was given to participants regarding proper mask use, nor were reminders made by the research staff on proper mask use. No blinding was used in this study.

Sample Size:

Assuming 50% baseline proper mask use, 58 participants per arm were needed to have 80% power to detect a 25% relative difference in proper mask adherence assuming a two-sided chi-square test and alpha = 0.05.

Measurements:

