At time of consent, a researcher assessed participants for their mask type, age, gender, race, ethnicity, Charlson Comorbidity Index (CCI)⁸, and chief complaint, which were then entered into a REDCap database. After randomization, the participants were reevaluated at 60 minutes by the same researcher, and the mask location (correct placement, on chin, nose exposed, mask removed, nose/mouth exposed) and patient disposition (admission/discharge) were recorded (Supplemental Figure 1). Participants were reevaluated without notice and were blinded as to why the investigator was entering the room.

Outcomes:

The primary outcome of this trial was proper mask utilization at 60 minutes assessed by a researcher. A subgroup analysis was performed comparing the frequency of correct mask wearing by mask type (hospital-provided versus patient-supplied masks).

Analysis:

Patient demographics and characteristics were compared between the control and treatment groups (self-reported) to ensure balance after randomization. To test for differences between groups on outcomes, Microsoft Excel (Microsoft Corporation, Redmond, WA) was used, and the Chi-square test (or Fisher's exact test for <5 counts) was used for categorical variables and the Wilcoxon test for continuous variables. All analyses were conducted by intention-to-treat.

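### Does the unspecified small-count trigger for Fisher's exact test cost the primary analysis power?

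*Combined protocol and SAP*

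**What the plan says.** The Analysis section names the chi-square test for categorical variables, with Fisher's "exact test for <5 counts" as the exception. It does not define the count. The same sentence covers the primary outcome, "proper mask utilization at 60 minutes assessed by a researcher", and the comparison by mask type described under Outcomes.

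The Sample Size section bases the trial on the chi-square test alone, "assuming a two-sided chi-square test and alpha = 0.05". Its other inputs are "Assuming 50% baseline proper mask use", "80% power to detect a 25% relative difference in proper mask adherence" and "58 participants per arm were needed".

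**The concern.** The chi-square approximation is usually judged by expected cell counts. A table can have one small observed cell while all its expected counts are comfortably at or above 5, and chi-square is then adequate. If the trigger means observed counts, such a table goes to Fisher's test, which is conservative.

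This looks awkward here because a small observed cell would most naturally be the number of taped patients with a misplaced mask. Success of the intervention would itself bring in the more conservative test, although the trial was sized for the other one. Some tables do change sides of 0.05. With 12 misplaced masks in the control arm and 4 in the tape arm, chi-square gives p = 0.031 and Fisher gives p = 0.057. At stake would be a loss of power for the primary outcome and a test chosen by the outcome data.

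**Working it through.** **Inputs.** From Sample Size: control proper use 50%, two-sided alpha 0.05, power 80%, 58 per arm. From Analysis: the Fisher trigger at counts below 5. Equal arms are taken from the single per-arm figure. Control rates other than 50%, all tape-arm rates, and subgroup sizes are assumptions.

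**Step 1: the plan's own figure.** With pooled variance under the null,

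n = [1.960 √(2p̄(1−p̄)) + 0.842 √(p₁(1−p₁) + p₂(1−p₂))]² / (p₂−p₁)²

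- 50% against 75%: p̄ = 0.625, so n = (1.342 + 0.557)² / 0.0625 = 57.7, which rounds up to 58.
- 50% against 62.5% (25% relative, as worded): p̄ = 0.5625, so n = (1.375 + 0.586)² / 0.015625 = 246.1, which rounds up to 247.

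The 58 per arm therefore corresponds to 25 percentage points. The label "25% relative difference in proper mask adherence" is a separate matter and does not affect the present question, since both effect sizes are checked below.

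**Step 2: the two readings.** Rule A uses Fisher if any observed cell is below 5. Rule B uses Fisher only if any expected cell is below 5. Both otherwise use chi-square without continuity correction and reject at p ≤ 0.05. For each pair of true rates, power is the sum, over all 2×2 tables with 58 per arm, of the binomial probability of each table that is rejected.

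**Step 3: which tables change.** With fewer misplaced masks under tape and a tape count below 5, the decision differs for four tables:

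| Misplaced, control / tape | Smallest expected count | Chi-square p | Fisher p |
|---|---|---|---|
| 8 / 2 | 5.0 | 0.047 | 0.094 |
| 9 / 2 | 5.5 | 0.027 | 0.053 |
| 10 / 3 | 6.5 | 0.039 | 0.074 |
| 12 / 4 | 8.0 | 0.031 | 0.057 |

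The only other tables that change are mirror images (arms exchanged, or proper and misplaced exchanged).

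Worked case, 12 / 4: chi-square = 116 × (12×54 − 4×46)² / (58 × 58 × 16 × 100) = 4.64, p = 0.031.

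These four tables imply control adherence between 46/58 = 79% and 50/58 = 86%. At the planned 50%, 29 misplaced masks are expected among 58 controls. The chance of 12 or fewer is about 4 in a million.

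**Step 4: power at the plan's 50% baseline.**

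| True proper use under tape | Chance that rule A uses Fisher | Power, rule A | Power, rule B |
|---|---|---|---|
| 62.5% | 0.0000 | 0.272 | 0.272 |
| 75% | 0.0004 | 0.799 | 0.799 |
| 85% | 0.05 | 0.988 | 0.988 |
| 90% | 0.30 | 0.999 | 0.999 |
| 95% | 0.84 | above 0.9999 | above 0.9999 |

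When tape works well from a 50% baseline, the observed-count trigger fires often, but the arms then differ so much that either test rejects. At 95% the two powers differ by about one in a million.

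**Step 5: power if control use were higher (assumed).**

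| Control / tape proper use | Power, rule A | Power, rule B |
|---|---|---|
| 60% / 95% | 0.9987 | 0.9989 |
| 70% / 90% | 0.791 | 0.797 |
| 75% / 93% | 0.749 | 0.784 |
| 80% / 95% | 0.623 | 0.711 |

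**Step 6: type I error.** With true use of 90% in both arms (assumed), the rejection rate is 0.022 under rule A and 0.045 under rule B. Neither exceeds 0.05.

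**The case for a change.** The strongest case for acting is that the 50% baseline is itself an assumption. Under Selection of Participants, facial coverings were compulsory by hospital policy. Under Interventions, participants were told that the study concerned PPE. Control adherence well above 50% is therefore plausible, and at 75% or more the loss is real: 3.6 points at 75% against 93%, and 8.8 points at 80% against 95%. The mask-type comparison follows the same rule with smaller numbers. Subgroup sizes are not given. If it is read as tape against control within mask type, with control use at 50% and tape at 75% to 95%, the observed-count reading costs about 0.6 to 2.2 points at an assumed 29 per arm, and about 3 to 10 points at an assumed 15 per arm. Adding one word would settle the meaning.

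The arithmetic stands, and so does the ambiguity. The inference to a faulty rule does not. The text never says observed, and the familiar condition it abbreviates concerns expected counts. The losses depend on control rates or subgroup sizes that the documents do not give. Even on the less favourable reading the rule errs towards caution, and choosing Fisher's test when a cell is small is a position that competent statisticians hold. The document also describes a completed analysis in the past tense, so a change now towards the less conservative test would not be free of objection.

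**Conclusion.** No change is called for. The trigger is loosely worded, and an analyst would ordinarily take it to mean expected counts. On the plan's own assumptions (58 per arm, 50% control use) the two readings give the same primary-outcome power to three decimals, whether tape reaches 62.5%, 75% or 95%. It is therefore not correct that power is lost simply because tape works well; the loss requires high adherence without tape.

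A material difference of roughly 4 to 9 points appears in the scenarios checked with control use of 75% to 80%, and up to about 10 points in subgroups of 15 per arm. All of these are assumed figures. On either reading, type I error in the sparse case checked stays below 0.05. The conclusion rests on equal arms, chi-square without continuity correction, and the 50% baseline. If control adherence were in fact near 80%, a p-value close to 0.05 could depend on the reading, and a report that names the test behind each p-value would make that visible.
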